#### **6.1.5. Multicenter Studies**

All investigative sites with fewer than 2 patients randomized to each treatment group (each patient with non-missing change from baseline in BPI average pain severity rating score) will be pooled together within each country and considered a single site for analyses. If this results in a “site” still having fewer than 2 patients randomized to each treatment, these sites will be pooled together with the next smallest site in that country. If there are no other sites in that country, then these sites would be pooled with the next smallest site in the whole study. All analyses will use pooled investigative sites. The actual investigative site numbers will be included in the listings.

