## **5.2. Determination of Sample Size**

Approximately 184 patients will be randomized in a 1:1 ratio to the duloxetine and placebo treatment groups. This study is to assess the difference of the mean change in BPI average pain severity from baseline to the last time point (Visit 8, Week 13) in Study Period II between treatment groups. Assuming that there will be some missing post-baseline data, and about 81% completion rate at acute phase by Visit 8 or Week 13, this sample size will provide at least 80% power to detect the treatment difference of 1.0 point with  $\alpha=.05$ . All the parameters used in the sample size calculations were based on the MMRM analysis of data from 3-month, placebo-controlled, acute treatment period in 2 adult FM studies: Study F1J-MC-HMCA and Study F1J-MC-HMCJ.

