A repeated measures analysis refers to a restricted maximum likelihood (REML)-based, mixed-effects repeated measures (MMRM) analysis using all the longitudinal observations at each post-baseline visit. The model for this analysis will include the fixed categorical effect of treatment, pooled investigative site, visit, and treatment-by-visit interaction, as well as the continuous, fixed covariate of baseline value of the variable being analyzed and baseline value of the variable being analyzed-by-visit interaction. An unstructured covariance structure will be used to model the within-patient errors. And Kenward-Roger approximation (Kenward and Roger, 1997) will be used to estimate denominator degrees of freedom. If the default Newton-Raphson algorithm used by SAS PROC MIXED does not converge, then the Fisher scoring algorithm will be applied.

However, if the model with unstructured covariance structure still fails to converge, the sandwich estimator (Diggle, Liang, and Zeger, 1994; Lu and Mehrotra, 2009) will be used to estimate the standard errors of the fixed effects parameters and the model will be fitted using covariance structures in the following order until convergence is met:

heterogeneous toeplitz	type = toeph
heterogeneous autoregressive (1st order)	type = arh(1)
heterogeneous compound symmetric	type = cs(h)
toeplitz	type = toep
autoregressive (1st order)	type = ar(1)
compound symmetric	type = cs

When the sandwich estimator is used, the Kenward-Roger approximation for denominator degrees of freedom cannot be used. Instead, the denominator degrees of freedom will be partitioned into between-subject and within-subject portions (denoted by DDFM= BETWITHIN in the MODEL statement).

For repeated measures analyses of efficacy and safety variables that are not collected at each post-baseline visit, data may exist at visits where the variable was not scheduled to be collected due to early discontinuation visits. Data collected at scheduled visits and early discontinuation visits will be used in the analysis. In these situations, the data from the early discontinuation visit will be carried forward to the next regularly scheduled collection visit for the repeated measures analysis. Significance tests will be based on least-squares means (LSMean) and Type III sum-of-squares, using a two-sided  $\alpha=0.05$ . Analyses will be implemented using SAS® PROC MIXED.

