The same MMRM, ANOVA and ANCOVA models excluding treatment effect will be used to present data for Study Period III, where appropriate.

Unless otherwise specified, for all analyses using the last-observation-carried forward (LOCF) approach in Study Period II, endpoint is defined as the last nonmissing observation obtained from Visit 3 through Visit 8; for the analyses using LOCF in Study Period III, endpoint is defined as the last nonmissing observation from Visit 9 through Visit 15.

In the analyses of some efficacy variables for Study Period II, the baseline-observation-carried-forward (BOCF) approach is considered. The BOCF endpoint is defined as follows:

For randomized patients who complete the treatment period (that is, complete the scheduled Visit 8) and have last nonmissing value at Visit 8, the BOCF endpoint is defined as the last nonmissing observation, for randomized patients who discontinue early (that is, do not complete the scheduled Visit 8) but with at least one non-missing baseline value, the BOCF endpoint is defined as the baseline value.

Categorical comparisons between treatment groups will be performed using Cochran-Mantel-Haenszel (CMH) test controlling for pooled investigative site and Fisher's exact test for Study Period II, when appropriate. For the categorical data, the number and percentage of patients for the categorical variables will be presented for Study Period III.

Where appropriate, variables will be summarized descriptively (frequency and percent will be summarized for categorical variables; number of patients with a non-missing observation, mean, SD, median, minimum, and maximum will be summarized for continuous variables) by study visit.

For those data summaries accompanied by individual patient data listings, data will be sorted by investigator ID, patient ID, and visit or event number if it is available.

Changes made to the data analysis methods will not necessarily require a protocol amendment and will be described in an updated SAP and reflected in the final report.

Statistical analysis of this study will be the responsibility of Eli Lilly and Company or designee. SAS® software will be used to perform most or all statistical analyses.

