### **6.1.3. Adjustments for Covariates**

In general, when a repeated measures analysis is used, the model will include the fixed categorical effect of treatment, pooled investigative site, visit, treatment-by-visit interaction, and the continuous, fixed covariates of the baseline value of the variable being analyzed and baseline value of the variable being analyzed-by-visit interaction. The baseline value of the variable being analyzed and the baseline value of the variable being analyzed-by-visit interaction are included to account for the differing influence over time of the baseline score on the post-baseline scores.

When an analysis of covariance (ANCOVA) model is used to analyze a continuous variable, the model will contain the main effects of treatment, pooled investigative site, and appropriate baseline values included as covariates.

Data presentations for Study Period III will be based on the same MMRM and ANCOVA models excluding treatment effect, where appropriate.

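### The extension-phase models drop treatment but keep pooled site, so default LS-means weight every pooled site equally; observed-margin weights would be at least as precise at almost no cost

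*SAP*

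**What the plan says.** Section 6.1.2 defines the MMRM with treatment, pooled site, visit, treatment-by-visit, baseline and baseline-by-visit as fixed effects, fitted in PROC MIXED, and adds: "Significance tests will be based on least-squares means (LSMean) and Type III sum-of-squares". The same section bases ANOVA and ANCOVA main-effect comparisons on Type III LS-means. For ANCOVA, Section 6.1.3 says "the model will contain the main effects of treatment, pooled investigative site, and appropriate baseline values included as covariates".

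For the extension, Section 6.1.2 says: "The same MMRM, ANOVA and ANCOVA models excluding treatment effect will be used to present data for Study Period III, where appropriate". Section 6.1.3 repeats it: "Data presentations for Study Period III will be based on the same MMRM and ANCOVA models excluding treatment effect, where appropriate". Only treatment is removed.

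Section 6.1.5 pools small sites, namely "All investigative sites with fewer than 2 patients randomized to each treatment group", counting patients with a non-missing change in BPI average pain. It sets a minimum size per randomized arm and no maximum, and does not reapply the rule after Study Period II dropout. Its statement that "All analyses will use pooled investigative sites" says which site variable is used, not how sites are weighted.

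Such models are actually planned. Section 6.1.14.3 specifies ANCOVA and MMRM for Study Periods II, III and II/III separately (MMRM for vital signs and weight; ANCOVA also for height), with within-treatment tests of change. Section 6.1.14.4 specifies ANCOVA for ECG in the same periods. No section states observed-margin or any other weights for LS-means.

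**The concern.** In Study Period II the site term adjusts a comparison between arms, and an additive site effect drops out of the difference, so the weighting of sites does not matter. In Study Period III, and in Study Period II/III where only the duloxetine group is analysed, there is no arm contrast. The reported quantity is a single mean change, and the weights define it.

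With default LS-means, a pooled site that ends with one or two patients counts as much as the largest site. Suppose 75 DLX/DLX patients in 20 pooled sites (20 is assumed): the only remaining patient at a site carries weight 1/20 instead of 1/75, which is 3.75 times as much. The extension-phase mean is then an average over sites, not over treated patients. It is less precise whenever site sizes differ, and a few patients at the smallest sites can move it.

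**Working it through.** **Inputs from the SAP.** Section 5.2: "Approximately 184 patients will be randomized in a 1:1 ratio to the duloxetine and placebo treatment groups", and "about 81% completion rate at acute phase by Visit 8 or Week 13". That implies 184 x 0.81 = 149 patients entering Study Period III, or about 75 per former arm. The number of sites, their sizes and the SD are not given.

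**The plan's own figure.** The SAP states no precision for Study Period III. The sample size of 184 cannot be reproduced without an SD, but one can be back-solved for scale. With 92 x 0.81 = 74.5 per arm, 80% power and a 1.0-point difference, SD = 1 / [(1.960 + 0.842) x sqrt(2/74.5)] = 2.18.

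**Formula.** For K pooled sites of size n_k, N = sum of n_k and residual SD s (one-way layout, baseline at its mean):

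- equal-site LS-mean: SE = (s/K) x sqrt(sum of 1/n_k)
- patient-weighted mean: SE = s / sqrt(N)
- ratio = sqrt(N x sum of 1/n_k) / K

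By the Cauchy-Schwarz inequality, N x (sum of 1/n_k) is at least K squared. The ratio is therefore never below 1, and equals 1 only when all pooled sites have the same size.

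**Example layouts (assumed).**

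| Pooled sites | N | Sum of 1/n_k | K | Ratio |
|---|---|---|---|---|
| 20 of 7 | 140 | 2.857 | 20 | 1.00 |
| 10 of 4 and 10 of 10 | 140 | 3.500 | 20 | 1.11 |
| 15 of 4 and 5 of 18 | 150 | 4.028 | 20 | 1.23 |
| 10 of 2 and 5 of 10 | 70 | 5.500 | 15 | 1.31 |

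**Simulation (assumed).** Settings: 184 patients, 15 to 40 sites, gamma-distributed enrolment (shape 0.7 to 5), 1:1 allocation within site, the Section 6.1.5 pooling rule with two countries, 81% retained, and 400 runs per setting. The median ratio across settings was 1.11-1.29 for both groups together and 1.13-1.31 for DLX/DLX alone. The lowest 5th percentile was about 1.06 and the highest 95th percentile about 1.62. Study Period II/III was not simulated; it includes duloxetine patients who stopped early, so 81% retention does not apply there.

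**Scale, at the back-solved SD.** With 149 patients the patient-weighted SE is 2.18 / sqrt(149) = 0.179, against 0.196 at a ratio of 1.10 and 0.232 at 1.30. With 75 patients it is 0.252, against 0.277 and 0.327.

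**If sites truly differ.** Fitting site then lowers the residual SD. At an assumed intraclass correlation of 0.10 the factor is sqrt(0.90) = 0.949, so against a plain patient mean with site omitted, 1.10-1.30 becomes about 1.04-1.23. Against an observed-margin LS-mean with site kept, both have the same residual SD and the full ratio remains.

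**The case against.** Several points on the other side stand.

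- Equal weighting is a software default that the SAP leaves in place, not a rule it states, and both carry-over sentences apply only where appropriate.
- A site-averaged mean is a legitimate summary, and keeping the same adjustment makes the two phases consistent.
- A model-based mean that differs from the raw mean is no defect in itself.
- The site term does more than change weights: it can remove between-site variance.
- Patient-weighted results are already planned. Section 6.1.13.2 summarises the Study Period III efficacy variables descriptively, and Section 6.1.14 says Study Period III safety is descriptive only, although 6.1.14.3 and 6.1.14.4 then plan models.

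A reader might infer more than the documents support.

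- **A fixed loss for this trial, such as 13-28%.** No site sizes are given, and equal pooled sites would give none.
- **A compromised maintenance conclusion.** Section 6.1.13.2 names a t-statistic and a confidence bound against the 1.5 margin, not a site-adjusted LS-mean.
- **Affected Study Period II/III pain results.** The carry-over sentences name Study Period III only, and the pain measures for II/III are mainly summarised descriptively.

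What remains is that vital signs, weight and ECG are to be modelled without an arm contrast. Following the text with default settings gives each pooled site equal weight, although an estimate at least as precise is available from the same model.

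**Conclusion.** The point holds as a low-severity improvement. It concerns model-based extension-phase means: vital signs, weight and ECG in Study Periods III and II/III, and any Study Period III efficacy result taken from the treatment-free models. Their standard error is never smaller than that of a patient-weighted mean at the same residual SD. The loss is 0% with equal pooled sites and typically about 10-30% in standard error under the assumed unequal layouts, with a tail to about 60%. The exact ratio is for a one-way layout; covariates and missing visits make it approximate. The SAP also does not say whether the Study Period III model is fitted per group or to both groups together, which is why both ranges are given. The primary Study Period II contrast is unaffected, and no decision rule in the plan is shown to change.

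**What to change.** Add to Section 6.1.2, with a cross-reference in 6.1.5: for models without a treatment term (Study Period III, and Study Period II/III where a model is used), pooled site is kept as a fixed effect and LS-means are computed with observed margins (the OM option), so that each patient counts equally. For the MMRM, take the margins from one record per patient, so that patients with more visits do not gain weight. The Study Period II between-arm models stay as they are.

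The cost is a short addition to the text and one option in the code, with no further data. The downside is that extension-phase LS-means would be weighted differently from the Study Period II arm LS-means unless observed margins are used for both; an additive site effect cancels from the Study Period II contrast under either weighting.

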#### **6.1.6. Multiple Comparisons/Multiplicity**

The primary efficacy analysis will be the contrast between duloxetine and placebo in the BPI average pain score change from baseline to endpoint (week 13) in Study Period II from a repeated measures analysis. No adjustments will be made for multiple comparisons.

#### **6.1.7. Patient Disposition**

The number and percentage of randomized patients who complete the study or discontinue early will be tabulated for all treatment groups for Study Period II, Study Period III, and Study Period

IV both overall and by visit. Reasons for discontinuation presented for Study Period II will be compared between treatment groups using Fisher's exact test. Reasons for discontinuation presented for Study Period III and Study Period IV will be summarized by treatment group.

Patient disposition data from all study periods will be listed.

### **6.1.8. Patient Characteristics**

Patient allocation by investigator, grouped by country, will be summarized for Study Period II for all ITT patients.

Patient allocation by investigator will also be listed for all ITT patients.

The following patient characteristics will be summarized by treatment group for all ITT patients for Study Period II, and for those ITT patients entering the Study Period III.

- Demographic information: age, gender, ethnicity, race origin, country, height, weight, and BMI
- Baseline comorbid diagnoses: MDD, GAD, and ADD
- Baseline severity of illness measured by: BPI severity and interference ratings, PPQ pain ratings, CGI-Severity: Mental Illness, CGI-Severity: Overall Illness, FDI-child, and FDI-parent, CDI, and MASC
- Medical history: duration of fibromyalgia (years); onset of fibromyalgia (age); presence of fibromyalgia in family history (yes/no)
- Pre-existing conditions
- Historical alcohol and tobacco consumption
- Baseline concurrent/ongoing therapies for FM symptoms: 1) NSAIDS, 2) Physical therapy, and 3) Psychotherapy
- Historical illnesses
- Onset of menses (female patients only): incidence prior to or post study entry among female patients; age of onset of first menses, defined as (date of first menses)-(date of birth)

Baseline concurrent/ongoing therapies are those therapies which are started, ongoing or stopped at baseline (visit 1 to 2). Baseline concurrent/ongoing therapies include psychotherapy, physical therapy, and NSAIDs.

Comparisons between treatment groups will be performed using Fisher's exact test for categorical data and ANOVA with treatment and pooled investigative site as independent variables in the model for continuous data for Study Period II. Patient characteristics will be summarized for Study Period III without any statistical comparison between treatment groups.

A listing of patient demographic characteristics will be presented.

The pre-existing conditions table will present the number and percent of patients with pre-existing conditions by preferred term in decreasing frequency within MedDRA system organ class. Pre-existing conditions for ITT patients in Study Period II and all ITT patients entering

Study Period III are events reported at baseline (visit 1 to 2) regardless if they are resolved or ongoing at the time of randomization.

The baseline historical illness table will summarize all significant illnesses reported at visit 1 by MedDRA preferred term and treatment group for all ITT patients for Study Period II and for those ITT patients entering Study Period III.

### 6.1.9. Significant Protocol Deviations

Significant protocol deviations will be listed for all Study Periods. The significant protocol deviations are defined in Table HMGW.6.2.

**Table HMGW.6.2 Definition of Significant Protocol Deviations**

Category of Protocol Deviation	Details	Methods of Checking
Improper administration of ICF	ICF not signed prior to initiation of protocol procedures	For all patients, if ICF (including assent form if applicable) date is after Visit 1 date or Visit 1 lab date, then result is a protocol deviation.
Inclusion/exclusion criteria	Randomized patient <13 years old at study entry	For randomized patient, if age<13 at ICF date, then result is a protocol deviation [criterion 1]
	Randomized patient >=18 years old at study entry	For randomized patient, if age >=18 at Visit 1 date, then result is protocol deviation [criterion 1]
	Randomized patient does not meet criteria for primary JPFS as defined by Yunus and Masi	For randomized patient, if JPFS criteria are not met at Visit 1, then result is protocol deviation. [criterion 2]
	Randomized patient does not have a score of ≥4 on BPI average pain severity at Visit 1 and Visit 2	For randomized patient, if BPI item #3 <4 at Visit 1 or Visit 2, then result is protocol deviation. [criterion 3]
	Randomized female patient tested positive for pregnancy	For randomized female patients, if pregnancy test is positive any time prior to Visit 2, then result is protocol deviation.

	[criterion 4]
Randomized patient had current diagnosis of <XXX> at study entry	For randomized patients, use Pre-existing conditions and study adverse event module. If there exists a current diagnosis of rheumatoid arthritis, arthritis, lupus, ankylosing spondylitis, psoriasis, then result is protocol deviation. [criterion 17]
Randomized patient had current diagnosis or diagnosis within 1 year of <XXX> at study entry	For randomized patients, use Pre-existing conditions and study adverse event module. If there exists a current diagnosis or diagnosis within 365 days (1 year) prior to visit 1 of bipolar disorder, psychotic depression, schizophrenia or other psychotic disorder, anorexia, bulimia, obsessive compulsive disorder, posttraumatic stress disorder, panic disorder, pervasive development disorder, then result is protocol deviation. [criterion 18]
Randomized patient had previous diagnosis of <XXX> at study entry	For randomized patients, use historical illness module. If there exists a previous diagnosis of bipolar disorder, psychotic depression, schizophrenia, schizoaffective disorder or other psychotic disorder, substance abuse or dependence (excluding caffeine and nicotine ) (in the past 183 days (6 months) prior to Visit1), seizure disorder excluding febrile seizures, then result is protocol deviation. [criterion 20, 22, 28]
Baseline weight < 20 kg for randomized patient	For randomized patients, if weight < 20 kg at Visits 1 or 2, then result is protocol deviation. [criterion 26]
Randomized patient treated with stimulant or other ADHD medication: <medication name> during screening.	For randomized patients, if patient has continued use of stimulant (eg, methylphenidate, amphetamine, lisdexamfetamine) or atomoxetine at Visit 1 or therapy end date after ICF date, then result is protocol deviation. [criterion 19,

		29]
	Randomized patient treated with MAOI : <medication name> <14 days of visit 1	For randomized patients, if DOV for visit 1 minus therapy end date for MAOI (e.g. isocarboxazid, phenelzine, selegilin, tranylcypromine) <14 days, then result is protocol deviation. [criterion 31]
	Randomized patient treated with fluoxetine <30 days of completion of visit 1	For randomized patients, if DOV for visit 1 minus therapy end date for fluoxetine <30 days, then result is protocol deviation. [criterion 30]
	Randomized patient treated with duloxetine < 6 months prior to visit 1	For randomized patients, if DOV for visit 1 minus therapy end date for duloxetine < 183 days (6 months), then result is protocol deviation. [criterion 14]
	Positive UDS prior to randomization (Visit 2).	For randomized patients if prior to visit 2 a patient has a positive UDS result and a repeated UDS not done or last repeat UDS is positive or UDS never collected, then result is protocol deviation. [criterion 23]
	Have uncontrolled narrow-angle glaucoma or acute liver injury at baseline	For randomized patients, use pre-existing/AE module. [criterion 33,34]
	Randomized patient treated with MAOI during study	For randomized patients, taking MAOI anytime > or = visit 2, then result is protocol deviation. [criterion 31]
Study Conduct – Concomitant Medications	Randomized patient reported prohibited concomitant medication use: <concomitant medication name>	For randomized patients, if any excluded medication (eg, SSRI, SNRI, stimulant, antipsychotic, benzodiazepine, anticonvulsant) is reported after Visit 2, then result is protocol deviation. Specify which concomitant medication in the protocol deviation details. Provide one record per patient per concomitant medication.
	Randomized patient who had consecutive use of NSAID less	For randomized patients in Study Period II, if patients had consecutive use of NSAID <

	
than 1 month immediately prior to visit 2 reported NSAID use: <NSAID name> exceeded 3 consecutive or exceeded 20 cumulative days during Study Period II
	
30 days (1 month) immediately prior to visit 2, and reported NSAID use exceeds 3 consecutive days or exceeds 20 cumulative days after visit 2 in SP II, then result is protocol deviation. Specify which NSAID in the protocol deviation details.

	
Randomized patient who had consecutive use of NSAID less than one month immediately prior to visit 8 reported NSAID use : <NSAID name> exceeded 3 days or exceeded 40 cumulative days during Study Period III
	
For randomized patients in Study Period III, if patients had consecutive use of NSAID < 30 days (1 month) immediately prior to visit 8, and reported NSAID use exceeds 3 consecutive days or exceeds 40 cumulative days after visit 8 in SP III, then result is protocol deviation. Specify which NSAID in the protocol deviation details.

	
Randomized patient reported opiate use : <opiate name> exceeded 3 consecutive or exceeded 20 cumulative days during Study Period II
	
For randomized patients in study Period II, opiate use exceeds 3 consecutive days or exceeds 20 cumulative days then result is protocol deviation. Specify which opiate in the protocol deviation details.

	
Randomized patient reported opiate use : <opiate name> exceeded 3 days/month or exceeded 40 cumulative days during Study Period III
	
For randomized patients in study Period III, opiate use exceeds 3 days/month or exceeds 40 cumulative days then result is protocol deviation. Specify which opiate in the protocol deviation details.

Study Conduct - Compliance	
Randomized patient took <80% or >120% of study drug for >= 2 visit intervals
	
For randomized patients, if <80% or >120% of study drug is taken >= 2 visits (consecutive or non-consecutive), then result is protocol deviation.

Study Conduct – Key measurements not collected	Missing key efficacy measurement: <BPI average pain score, CGI-S overall illness>	For randomized patients, if BPI average pain severity or CGI-S overall illness is missing at any scheduled visit, then result is protocol deviation. Provide one record per patient per missing measurement per visit.
	Missing safety measurement: <CSSRS, Blood Pressure, Pulse, Height, Weight, Labs, ECGs>	For randomized patients, if C-SSRS, blood pressure, pulse, height, weight, are missing at any scheduled baseline or post-baseline visits at or before the early discontinuation visit, then result is protocol deviation. Provide one record per patient per missing measurement per visit.  For ALT lab test, if any scheduled or unscheduled baseline labs are missing or if a patient discontinued at or after visit 6 (the first scheduled post-baseline visit for labs is visit 6), and without any scheduled or unscheduled post-baseline labs data, then it is a protocol deviation.  For ECG QTcF measure, if any scheduled or unscheduled baseline ECGs are missing or if a patient discontinued at or after visit 8 (the first scheduled post-baseline visit is visit 8), and without any post-baseline data, then it is a protocol deviation.
Visit interval outside specified limits	Visit interval length exceeds (number of days study drug dispensed + 2 days) (excluding taper phase)	For randomized patients, compare actual visit interval length to number of days study drug dispensed at each visit. Allowable visit interval lengths (resulting in no more than 2 days off drug):  Visit 2,3, 8: 11 days  Visit 4, 9: 20 days  Visit 5,6,7, 10: 29 days  Visit 11: 38 days  Visit 12,13: 47 days

		Visit 14: 56 days
--	--	-------------------

